|----------------------------------------------------------------------------------------------------------------------------------------------------------------------------------------------------------------------------------------------------------------------------------------------------------------------------------------------------------------------------------------------------------------------------------------------------------------------------------------------------------------------------|-------------------------------------------------------------------------------------------------------------------------------------------------------------------------------------------------------------------------------------------------------------------------------------------------------------------------------------------------------------------------------------------------------------------------------------------------------------------------------------------------------------------------------------------------------------------------------------------------------------------------------------------------------------------------------------------------------------------------------------------------------------------------------------------------------------------------------------------------|
| | 
administration
 
Part 2 (IV infusion)
 
 • The number and percentages of participants who have AEs and SAEs following GSK3810109 IV administration through Week 24 • The incidence of Grade 2 to 4 elevated ALT/AST following GSK3810109 IV administration through Week 24 |
| Secondary | |

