| PIN and NRS ⁶ | | | | X | | | X | | | X | | | | | | | | | | |
| 12-lead ECG ⁷ | X | | X | | X | | X | X | X | | | | X | | | | | X | | |
| Clinical laboratory ⁵ | X | X | | | | | X | | | X | X | | X | | | X | | X | X | |
| Urinalysis ⁵ | X | X | | | | | | | | X | | | | | | | | | | |
| Pregnancy test:(serum) (POCBP only) ⁸ | X | X | | | | | X | | | X | X | | X | X | X | X | X | X | X | |
| FSH ⁹ | X | | | | | | | | | | | | | | | | | | | |
| HIV and hepatitis B and C ⁵ | X | | | | | | | | | | | | | | | | | | | |
| Test for SARS-CoV-2 ¹⁰ | X | X | | | | | | | | | | | | | | | | | | |

| Visit Number | | | 01 | 01A | 01B | 01C | 02 | 03 | 04 | 05 | 06 | 07 | 08 | 09 | 10 | 11 | 12 | 13 | ED = early discontinuation/withdrawal | |
|---------------------------------------------------------------------------|--------------------------|----------|---------------------|-------------|-----|-----|------|------|------|-----|-----|-----------|-----|-----|------|------|------|------|---------------------------------------|--|
| Time From Start of SC Infusion | | | Pre | SOI | 4hr | 8hr | 24hr | 48hr | 72hr | Wk1 | Wk2 | Wk3 | Wk4 | Wk8 | Wk12 | Wk16 | Wk20 | Wk24 | | |
| Day of Study ¹ | | D-1 | D1 | D1 | D1 | D1 | D2 | D3 | D4 | D7 | D14 | D21 | D28 | D56 | D84 | D112 | D140 | D168 | | |
| Clinical Activity | Screen Days -21 to -2 | Check-in | Intervention Period | | | | | | | | | Follow-up | | | | | | | | |
| Timed PK sample ¹¹ | | | X | X | X | | X | X | X | X | X | X | X | X | X | X | X | X | | |
| CCI [REDACTED] sample collection | | | X | | | | | | | | | | X | X | X | X | X | X | | |
| Recording of injection site reactions in 14 days diary card ¹² | | | | ←————→————— | | | | | | | | | | | | | | | | |
| Recording of AEs/SAEs ¹³ | | | | ←————→————— | | | | | | | | | | | | | | | | |
| Concomitant medication review | | | X | X | X | | X | X | X | X | X | X | X | X | X | X | X | X | | |

AE = adverse event; BMI = body mass index; COVID-19 = coronavirus disease; FSH = follicle-stimulating hormone; HIV = human immunodeficiency virus-1; ISR = injection site reaction; NRS = Numeric Rating Scale; PIN = Perception of Injection PK = pharmacokinetic(s); POCBP = participant of childbearing potential; SAE = serious adverse event; SARS-CoV-2 = severe acute respiratory syndrome-related coronavirus-2; SC = subcutaneous; SOI = start of infusion

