1.6. Schedule of Activities (SoA) (Part 2)

| Visit Number | | | 01 | 01A | 01B | 01C | 02 | 03 | 04 | 05 | 06 | 07 | 08 | 09 | 10 | 11 | 12 | 13 | 14 | 15 | ED = early discontinuation/withdrawal |
|--------------------------------------------------------|--------------------------|----------|---------------------|-----|-----|-----|------|------|------|-----|-----|------------------|-----|-----|-----------|-----|------|------|------|------|---------------------------------------|
| Time From Start of IV Infusion | | | Pre | EOI | 4hr | 8hr | 24hr | 48hr | 72hr | Wk1 | Wk2 | Wk2 | Wk2 | Wk3 | Wk4 | Wk8 | Wk12 | Wk16 | Wk20 | Wk24 | |
| Day of Study ¹ | | D-1 | D1 | D1 | D1 | D1 | D2 | D3 | D4 | D7 | D8 | D10 ² | D14 | D21 | D28 | D56 | D84 | D112 | D140 | D168 | |
| Clinical Activity | Screen Days -21 to -2 | Check-in | Intervention Period | | | | | | | | | | | | Follow-up | | | | | | |
| Informed consent | X | | | | | | | | | | | | | | | | | | | | |
| Admission to clinic | | X | | | | | | | | | | | | | | | | | | | |
| Discharge from clinic | | | | | | | | | | | X | | | | | | | | | | |
| Inclusion and exclusion criteria | X | X | | | | | | | | | | | | | | | | | | | |
| Demographics | X | | | | | | | | | | | | | | | | | | | | |
| Height, weight, and BMI ³ | X | X | X | | | | | | | | | | | | | | | | | | |
| Vital signs ⁴ | X | X | X | | X | X | X | X | X | X | X | X | X | X | X | X | X | X | X | X | |
| Physical examination ⁵ | X | X | X | X | | X | | | | | | X | | | | | | | | X | |
| Drug Alcohol/Cotinine /history and screen ⁶ | X | X | | | | | | | | | | | | | | | | | | | |

| Visit Number | | | 01 | 01A | 01B | 01C | 02 | 03 | 04 | 05 | 06 | 07 | 08 | 09 | 10 | 11 | 12 | 13 | 14 | 15 | ED = early discontinuation/withdrawal |
|-----------------------------------------------------|--------------------------|----------|---------------------|-----|-----|-----|------|------|------|-----|-----|------------------|-----|-----|-----------|-----|------|------|------|------|---------------------------------------|
| Time From Start of IV Infusion | | | Pre | EOI | 4hr | 8hr | 24hr | 48hr | 72hr | Wk1 | Wk2 | Wk2 | Wk2 | Wk3 | Wk4 | Wk8 | Wk12 | Wk16 | Wk20 | Wk24 | |
| Day of Study ¹ | | D-1 | D1 | D1 | D1 | D1 | D2 | D3 | D4 | D7 | D8 | D10 ² | D14 | D21 | D28 | D56 | D84 | D112 | D140 | D168 | |
| Clinical Activity | Screen Days -21 to -2 | Check-in | Intervention Period | | | | | | | | | | | | Follow-up | | | | | | |

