| Past and Current medical conditions | X | X | | | | | | | | | | | | | | | | | | | |
| Study product administration ⁷ | | | | X | | | | | | | | | | | | | | | | | |
| NRS | | | | X | | | X | | | X | | | | | | | | | | | |
| 12-lead ECG ⁸ | X | | X | X | X | | X | X | X | X | X | X | | | X | | | | X | | |
| Clinical laboratory ⁶ | X | X | | | | | ↔ | | | | | X | X | | X | | X | | X | | X |
| Urinalysis ⁶ | X | X | | | | | | | | | | X | X | | | | | | | | |
| Pregnancy test:(serum) (POCBP only) ⁹ | X | X | | | | | X | | | X | | | X | | X | X | X | X | X | X | |
| FSH ¹⁰ | X | | | | | | | | | | | | | | | | | | | | |
| HIV and hepatitis B and C ⁶ | X | | | | | | | | | | | | | | | | | | | | |

| Visit Number | | | 01 | 01A | 01B | 01C | 02 | 03 | 04 | 05 | 06 | 07 | 08 | 09 | 10 | 11 | 12 | 13 | 14 | 15 | ED = early discontinuation/withdrawal | |
|-------------------------------------|--------------------------|----------|---------------------|-----|-----|-----|------|------|------|-----|-----|------------------|-----------|-----|-----|-----|------|------|------|------|---------------------------------------|--|
| Time From Start of IV Infusion | | | Pre | EOI | 4hr | 8hr | 24hr | 48hr | 72hr | Wk1 | Wk2 | Wk2 | Wk2 | Wk3 | Wk4 | Wk8 | Wk12 | Wk16 | Wk20 | Wk24 | | |
| Day of Study ¹ | | D-1 | D1 | D1 | D1 | D1 | D2 | D3 | D4 | D7 | D8 | D10 ² | D14 | D21 | D28 | D56 | D84 | D112 | D140 | D168 | | |
| Clinical Activity | Screen Days -21 to -2 | Check-in | Intervention Period | | | | | | | | | | Follow-up | | | | | | | | | |
| Test for SARS-CoV-2 ¹¹ | X | X | | | | | | | | | | | | | | | | | | | | |
| Timed PK sample ¹² | | | X | X | X | | X | X | X | X | | | X | X | X | X | X | X | X | X | X | |
| CCI | | | | | | | | | | | | | | | | | | | | | | |
| Recording of AEs/SAEs ¹³ | | | | | | | | | | | | | | | | | | | | | X | |
| Concomitant medication review | | | | | | | | | | | | | | | | | | | | | X | |

AE = adverse event; BMI = body mass index; COVID-19 = coronavirus disease; EOI = end of infusion; FSH = follicle-stimulating hormone; HIV = human immunodeficiency virus; IV = intravenous; NRS = Numeric Rating Scale; PK = pharmacokinetic(s); POCBP = participant of childbearing potential; SAE = serious adverse event; SARS-CoV-2 = severe acute respiratory syndrome-related coronavirus-2

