| Day of Study ¹ | D-1 | D1 | D1 | D1 | D1 | D2 | D3 | D4 | D7 | D14 | D21 | D28 | D56 | D84 | D112 | D140 | D168 | |
| Clinical Activity | Screen Days -21 to -2 | Check-in | Intervention Period | | | | | | | | | | | | Follow-up | | | |
| Informed consent | X | | | | | | | | | | | | | | | | | |
| Admission to clinic | | X | | | | | | | | | | | | | | | | |
| Discharge from clinic | | | | | | | | X | | | | | | | | | | |
| Inclusion and exclusion criteria | X | X | | | | | | | | | | | | | | | | |
| Demographics | X | | | | | | | | | | | | | | | | | |
| Height, weight, and BMI ² | X | X | X | | | | | | | | | | | | | | | |
| Vital signs ³ | X | X | X | | X | X | X | X | X | X | X | X | X | X | X | X | X | |
| Physical examination ⁴ | X | X | X | | | X | | | | | | | | | | | | X |
| Drug Alcohol/Cotinine /history and screen ⁵ | X | X | | | | | | | | | | | | | | | | |

| Visit Number | | | 01 | 01A | 01B | 01C | 02 | 03 | 04 | 05 | 06 | 07 | 08 | 09 | 10 | 11 | 12 | 13 | ED = early discontinuation/withdrawal |
|-----------------------------------------------------|--------------------------|----------|---------------------|-----|-----|-----|------|------|------|-----|-----|-----|-----------|-----|------|------|------|------|---------------------------------------|
| Time From Start of SC Infusion | | | Pre | EOI | 4hr | 8hr | 24hr | 48hr | 72hr | Wk1 | Wk2 | Wk3 | Wk4 | Wk8 | Wk12 | Wk16 | Wk20 | Wk24 | |
| Day of Study ¹ | | D-1 | D1 | D1 | D1 | D1 | D2 | D3 | D4 | D7 | D14 | D21 | D28 | D56 | D84 | D112 | D140 | D168 | |
| Clinical Activity | Screen Days -21 to -2 | Check-in | Intervention Period | | | | | | | | | | Follow-up | | | | | | |
| Past and Current medical conditions | X | X | | | | | | | | | | | | | | | | | |
| Study product administration ⁶ | | | | X | | | | | | | | | | | | | | | |
| PIN and NRS ⁷ | | | | X | | | X | | | X | | | | | | | | | |
| 12-lead ECG ⁸ | X | | X | | X | | X | X | X | X | | | X | | | | X | | |
| Clinical laboratory ⁵ | X | X | | | | | X | X | X | X | X | | X | | X | | X | X | |
| Urinalysis ⁵ | X | X | | | | | | | | X | | | | | | | | | |
| Pregnancy test:(serum) (POCBP only) ⁹ | X | X | | | | | X | | | X | X | | X | X | X | X | X | X | |
| FSH ¹⁰ | X | | | | | | | | | | | | | | | | | | |
| HIV and hepatitis B and C ⁵ | X | | | | | | | | | | | | | | | | | | |
| Test for SARS-CoV-2 ¹¹ | X | X | | | | | | | | | | | | | | | | | |

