| | 
fever occurred after IV or SC administration.
 
All reported instances of systemic reactogenicity (malaise, myalgia, headache, nausea, chills) were mild (Grade 1) and were reported as recovered within 1 day of onset.
 | |
| Gastrointestinal disorders (Diarrhea) | 
Non-clinical
 
Not applicable
 
Clinical
 
In the Phase 1 study, 3 participants experienced diarrhea (Grade 1 to Grade 3) considered related by the investigator. Time to onset was 1 to 6 days from last dose and all recovered within 2 days. One additional participant with Grade 1 diarrhea was not considered related (time to onset was 19 days post dose).
 | 
Careful monitoring of gastrointestinal AEs will occur throughout the study. Serious/severe events will be managed appropriately and will be followed to resolution as per standard ViiV Medical Monitoring practices.
 |
| Liver chemistry elevations | 
Non-clinical
 
The repeat-dose IV and SC administration of GSK3810109 at 40 and 400 mg/kg IV and 5 and 50 mg/kg SC in Sprague Dawley rats produced test article-related effects in clinical chemistry with up to 1.5-fold increase in AST, ALT and/or ALP, correlating with the histopathologic findings in the liver, within high-end of normal ranges and considered not to
 | 
Participants with liver impairment based on screening liver chemistry will be excluded:
 
Participants with ALT $> \times 1.5$ ULN or total bilirubin $> 1.5 \times$ ULN are excluded (Exclusion criteria #16 and #17).
 
Liver aminotransferases (ALT and AST) will be monitored throughout this study (refer to SoA,
 |

| Potential Risk of Clinical Significance | Summary of Data/Rationale for Risk | Mitigation Strategy |

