10.2. Appendix 2: Clinical Laboratory Tests

The tests detailed in [Table 2](#) will be performed by the central laboratory/the local laboratory.

Protocol-specific requirements for inclusion or exclusion of participants are detailed in [Section 5](#) of the protocol.

Additional tests may be performed at any time during the study as determined necessary by the investigator or required by local regulations.

Table 2 **Protocol-required Safety Laboratory Tests**

| Laboratory Assessments | Parameters | | | | | |
|---------------------------------|-----------------------------------------------------------------------------------------------------------------------------------------------------------------------------------------------------------------------------------------------------------------------------------------------------------------------------------------------------------------|-------------------------------------------------------------------------------------------------------------|--------------------------------------------------------|-------------------------------------------------------------------------------------------------------------------------|--|--|
| Hematology | Platelet count Red Blood Cell count Hemoglobin Hematocrit | Red Blood Cell Indices: Mean corpuscular volume Mean corpuscular hemoglobin % Reticulocytes | | White Blood Cell count with differential: Neutrophils Lymphocytes Monocytes Eosinophils Basophils | | |
| Clinical Chemistry ¹ | Blood Urea Nitrogen Creatinine Glucose (fasting) Potassium Sodium Chloride Calcium | Carbon dioxide AST ALT Alkaline phosphatase ² | Total and direct bilirubin Albumin Total protein | | | |
| Routine Urinalysis | 
 Specific gravity pH, glucose, protein, blood, ketones, bilirubin, urobilinogen, nitrite, leukocyte esterase by dipstick Microscopic examination (if blood or protein is abnormal on dipstick) | | | | | |
| Pregnancy testing | 
 Highly sensitive serum human chorionic gonadotropin (hCG) pregnancy test (as needed for women of childbearing potential) | | | | | |

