### **4.2. Primary Endpoint(s) Analyses**

#### **4.2.1. Definition of Endpoints**

The primary endpoints for this study are:

Part 1:

- The number and percentage of participants who have AEs (Grade 2 or higher) and SAEs following GSK3810109 administration through week 24.
- The number and percentage of participants who have ISRs within 7 days following GSK3810109 administration.
- The number and percentage of participants who experience Grade 2 to 4 ALT/AST following GSK3810109 administration.

Part 2:

- The number and percentages of participants who have AEs and SAEs following GSK3810109 IV administration through Week 24
- The incidence of Grade 2 to 4 elevated ALT/AST following GSK3810809 IV administration through Week 24.

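### Part 2 names Week 24 for its primary ALT/AST endpoint, but its schedule shows no routine laboratory draw for completers after Week 20

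*Protocol*

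**What the plan says.** **Endpoint.** The Part 2 list in the protocol Synopsis has "The incidence of Grade 2 to 4 elevated ALT/AST following GSK3810109 IV administration through Week 24". SAP Section 1.1 carries the same line, and SAP Section 4.2.1 closes its Part 2 endpoints with "IV administration through Week 24". The Synopsis gives no Week 24 limit to the ALT/AST endpoint of Parts 1 and 3.

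**Estimand and analysis.** In protocol Section 3 and SAP Section 1.1, the Part 2 estimand ties Week 24 to AEs and SAEs and then adds Grade 2 to 4 ALT/AST with no time limit. Protocol Section 9.3.2 and SAP Section 4.2.2 set no window for the ALT/AST count either.

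**Schedule.** ALT and AST belong to the chemistry panel in protocol Section 10.2 ("Carbon dioxide AST ALT Alkaline phosphatase"). Sections 4.1 and 8.1.4 leave the timing of safety laboratory tests to the Schedule of Activities. The last six day columns of the Part 2 table are "D28 | D56 | D84 | D112 | D140 | D168", followed by ED. The row that begins "Clinical laboratory ⁶ | X | X" is ticked under Day 140 and ED and blank under Day 168. No footnote or Section 8 text adds a Week 24 safety laboratory draw.

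**Stated intent.** The liver row of the risk table in Section 2.3.1 says "Liver aminotransferases (ALT and AST) will be monitored throughout this study" and refers to the schedules of all three parts.

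**The concern.** Part 2 is the only part whose ALT/AST endpoint names Week 24, and the only part whose laboratory row is blank there. It also gives the highest dose in the programme: the Synopsis says that no single administration has exceeded 40 mg/kg, and Part 2 gives 60 mg/kg.

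If the blank is real, the endpoint claims a period that the schedule does not routinely sample. A completer whose last chemistry was on Day 140 enters the numerator or denominator as though followed to Week 24, because SAP Section 4.2.2 has no rule on how late a participant must have been tested to count as free of an elevation. A participant who leaves early does get a closing draw through the ED column. Whether the end of a participant's follow-up carries an ALT/AST value would then depend on completion status.

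**Working it through.** **1. Check the column alignment.** The Part 2 header has 21 columns after the label: Screening, Check-in, 18 visit columns (01, 01A, 01B, 01C, and 02 to 15) and ED, so 2 + 18 + 1 = 21. The laboratory row also has 21 cells. Three features support the mapping:

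- The arrow and the four empty cells after it fill exactly Days 2, 3, 4, 7 and 8, which matches the amendment summary's Day 2 through Day 8 monitoring.
- The next tick falls on Day 10, where Section 4.1 needs laboratory data for the sentinel review.
- In the same table, vital signs, pregnancy tests and PK all reach Day 168.

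**2. Set the three schedules side by side.** The Part 1 row is the one beginning "Clinical laboratory ⁵ | X | X | | | | | X" in Section 1.5. The Part 3 row is the one beginning "Clinical laboratory ⁵ | X | X | | | | | X | X | X | X" in Section 1.7.

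| | Part 1 | Part 2 | Part 3 |
|---|---|---|---|
| Week 24 named for ALT/AST in the Synopsis | no | yes | no |
| Scheduled draws after Day 28 | Days 112, 168 | Days 84, 140 | Days 84, 140, 168 |
| Week 24 cell | ticked | blank | ticked |
| ED cell | ticked | ticked | blank |

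**3. Size of the gap for a Part 2 completer.** The inputs are Day 140 and Day 168 from the header and ±7 days for Visits 14 and 15 from the visit-window note.

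- Nominal: 168 − 140 = 28 days; 28/168 = 16.7% of follow-up.
- Shortest: (168 − 7) − (140 + 7) = 161 − 147 = 14 days.
- Longest: (168 + 7) − (140 − 7) = 175 − 133 = 42 days.

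**4. Compare with the earlier spacing.** 84 − 28 = 56 days and 140 − 84 = 56 days, both longer than the final gap. Those intervals are closed by a later draw, so an elevation that persists is still picked up. The interval after Day 140 has no closing draw for completers.

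**5. Granularity.** With about 8 participants, one participant is 1/8 = 12.5 percentage points. This is the step size of the reported percentage. It does not estimate what might be missed.

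**6. What a column slip would do.** If the last tick really belongs to Week 24, the Part 2 row ends as in Part 3: completers are covered and ED is blank. If a tick was lost and both cells are filled, the row ends as in Part 1 and nothing needs changing.

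**The case against.** The strongest objection is that everything turns on two adjacent end columns of a table read from PDF. A matching cell count does not prove placement there. The Part 2 physical examination row also has 21 cells, and its last tick falls under Week 24, whereas footnote 5 places that examination at ED and mentions none at Week 24. Part 1 shows the same conflict with its footnote 4. This stands, and it is why the PDF page must be checked first. It does not dispose of the point: one tick cannot serve both columns, so if it moves to Week 24, Part 2 withdrawals lose their closing draw, and Section 7.4 relies on the schedule for what to collect from them.

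Three stronger readings that a reader might infer are not supported:

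- *That nothing is observed after Week 20.* Only scheduled draws stop there. Section 8 allows unscheduled samples, Section 8.1.4 has clinically significant values repeated, Section 8.2.1 collects AEs to the last visit, and SAP Section 4.1 counts unscheduled results in the worst case. These sources are event-driven and do not give every completer a late value.
- *That every statement of the endpoint, or a planned table title, claims Week 24.* The estimand and analysis text sets no limit for ALT/AST, and the documents show no such table title.
- *That the blank Part 3 ED cell contradicts an endpoint.* It does not, since the Part 3 ALT/AST endpoint names no week.

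It is also fair to say that intermittent sampling is inherent in such an endpoint, and that the study is descriptive with no hypothesis test. Both stand as limits on the consequence.

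**Conclusion.** On the best reading of the Part 2 schedule, the primary ALT/AST endpoint runs through Week 24 in the Synopsis and SAP, while scheduled chemistry for completers ends at Week 20. The final nominal 28 of 168 days (16.7%; 14 to 42 days with visit windows) has no scheduled ALT/AST in completers, and only event-driven samples could contribute.

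This rests on the Week 24 and ED cells being correctly placed in the machine-read table. The row's width and its earlier ticks support that, but the physical examination row shows that it is not certain. The conclusion does not depend on a late elevation being likely, and the documents give no basis for estimating how many would be missed. It is an inconsistency between a primary endpoint definition and its measurement schedule, and it needs to be settled before the Part 2 results are reported.

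**What to change.** 1. Check the Week 24 and ED cells of the clinical laboratory row on the PDF page of protocol Section 1.6.
2. If Week 24 is blank and the visit is still ahead, tick clinical laboratory at Visit 15 (Day 168) and keep the ED tick. PK blood is already drawn at that visit, so the cost is one small extra tube and a schedule correction. The protocol caps blood at 500 mL per participant but gives no safety laboratory volumes, so the sponsor should confirm that the total still fits.
3. If Part 2 is already past that visit, restate the ALT/AST endpoint as running through the last scheduled laboratory visit (Week 20). Make the change consistently in protocol Sections 1.1 and 3 and SAP Sections 1.1 and 4.2.1. This costs wording only.
4. If the page shows the last tick under Week 24, the endpoint wording can stand, and the Part 2 ED cell is what needs resolving. If both cells are ticked, no change is needed.
5. Check the blank ED laboratory cell in the Part 3 schedule (Section 1.7) in the same correction, as a secondary item.

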1.2. Schema (Part 1)

[figure not shown]
N= 8; All participants will receive a single 20 mg/Kg SC dose of GSK3810109 co-administered with rHuPH20 and be followed up for 24-weeks

